Other secondary study endpoints will look at a variety of patient outcomes as well as best practice metrics, including the following:

- Inpatient mortality
- Inpatient dialysis
- Discharged on dialysis
- Percent who progress to stage 2 AKI
- Percent who progress to stage 3 AKI
- AKI duration
- 30-day readmission rate
- Cost of index hospitalization
- “Best practice” outcomes: Proportion achieved per patient during index hospitalization:
 - Contrast administration
 - Fluid administration
 - Aminoglycoside administration
 - NSAID administration/cessation
 - ACEi administration/cessation
 - Urinalysis order
 - Documentation of AKI
 - Monitoring of creatinine
 - Monitoring of urine output
 - Renal consults

All investigators will be blinded to the treatment assignment until the end of the trial period.

Clinician Outreach:

While the unit of randomization is the patient, clinicians are considered subjects of this research. We will engage in pre-trial and periodic outreach to all clinicians who may be exposed to this study, informing them of the nature of the study, the fact that it is a randomized trial, and that alerts do not fire for all patients with AKI. We will additionally inform them that limited data is being collected regarding provider behavior. However, we will also make it clear that data subject to clinician behavior (continuation or discontinuation of any medication) will NOT be linked to individual clinicians. All such data will only be analyzed in aggregate. This outreach will be performed through short presentations at divisional conferences and meetings and through regular visits to hospital floors to engage directly with providers. A study Information Sheet will also be handed out to clinicians.

Study Timeline:

We plan to activate our medication-targeted alert in a step-wise fashion throughout our 4 study hospitals. Staggered enrollment will allow for proper pre-trial education as well as adequate site visits, study monitoring, quality control and clinician engagement at each site as roll out begins.

5. Genetic Testing N/A

A. Describe

- i. the types of future research to be conducted using the materials, specifying if immortalization of cell lines, whole exome or genome sequencing, genome wide association studies, or animal studies are planned *Write here*
- ii. the plan for the collection of material or the conditions under which material will be received *Write here*

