- Under-treatment: Patients randomized to medication-targeted alerts may have these medications discontinued more often. This should be beneficial, as the medications chosen have been associated with AKI. But it is also possible that, in some situations, discontinuation of medicine might engender risk (for example, discontinuation of a proton-pump inhibitor among patients with a gastrointestinal bleed). The internal DSMB has identified the following risks of discontinuation for each medication class with an associated monitoring plan to ensure that differential discontinuation does not cause harm to patients:

Nephrotoxin	Risk(s) of Discontinuation	Monitoring Plan
NSAID	
 -Increased use of opioid analgesics -Worse pain 	
 -Morphine-equivalent opioid exposure per patient-day -Use of naloxone and/or naltrexone -Intubation -Nursing-reported pain score
ACE/ARB/Renin	
 -Hypertension -Pulmonary Edema -Heart Failure 	
 -Blood pressure -Intubation -Chest X-Rays

PPI	
 -GI Bleed -Pain -Severe anemia 	
 -Echocardiogram -Blood Transfusion -Endoscopy Procedures -Nursing-reported pain score
-----	--	--

- Inattention to AKI: It is possible that, as providers learn that alerts exist, they become less attentive to the presence of AKI in patients randomized to the usual care group. We limit this risk by including the language "THIS ALERT DOES NOT FIRE FOR ALL PATIENTS WITH AKI" in each alert. Additionally, our educational efforts (which target each hospital division before the trial and biannually after initiation) make explicit the fact that these alerts are being conducted in a randomized framework.

-Alert Fatigue: These studies represent an additional alert to which providers will be exposed and prior research has demonstrated that more frequent alerting may lead to less attention to other alerts. While a potential risk, this is also a major motivation of this line of research, as only via randomized trials can truly effective alerts be discovered. Should no effect be found in these studies, AKI alerts will not be continued at the institutions.

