- To minimize the risk of undertreatment, the internal DSMB has identified outcomes of interest for each of the medication classes to ensure that differential discontinuation is not causing harm and will utilize their authority to suspend an arm of the study should harm be detected. Additionally, medication-targeted alerts will contain language that illustrates patient populations wherein continuation of the medication may be warranted (please refer to Data and Safety Monitoring Plan document).
- To limit the risk of inattention to AKI, we include the following language on the alert screen: "THIS ALERT DOES NOT FIRE FOR ALL PATIENTS WITH AKI". Additionally, our educational efforts (which target each hospital division before the trial and biannually after initiation) make explicit the fact that these alerts are being conducted in a randomized framework.
- Based on the new information obtained from our recent general AKI alert study which showed signals of harm in the non-teaching hospitals, we are taking necessary precautions to maximize patient safety in this trial. This proposed trial does involve a unique and more specific population than that of our prior study, and utilizes a different intervention which offers more individualized recommendations and guidance for clinicians.

As a preliminary assessment of safety of our drug-targeted alert, we analyzed a subset of data from our initial alert trial, including only patients who meet criteria for the current study (those AKI patients who had at least one dose of one of our targeted nephrotoxic medications within the 24 hours prior to AKI development). The results, both overall and stratified by hospital, are shown below:

Outcome Table

Variables	Control (N=1244)	Alert (N=1250)	p-value
Primary Outcome			.
AKI Progression, Dialysis or Death	205 (16.5%)	234 (18.7%)	0.1379
Secondary Outcomes			.
AKI Progression	162 (13%)	194 (15.5%)	0.0762
Dialysis	29 (2.3%)	35 (2.8%)	0.4714
Death	73 (5.9%)	67 (5.4%)	0.6142
Discharge to Home	688 (55.3%)	660 (52.8%)	0.1791
Length of Stay, days after randomization	3.4 (1.6,7.7)	4 (1.9,8.2)	0.3585
Duration of AKI, days			0.8928
<2 days	926 (74.4%)	930 (74.4%)	.
2 - <7 days	275 (22.1%)	272 (21.8%)	.
7+ days	43 (3.5%)	48 (3.8%)	.
Max AKI Stage Achieved			0.8527
Stage 0	2 (0.2%)	2 (0.2%)	.
Stage 1	985 (79.2%)	982 (78.6%)	.
Stage 2	155 (12.5%)	165 (13.2%)	.
Stage 3	102 (8.2%)	101 (8.1%)	.

Outcome Table
YNH

Variables	Control (N=462)	Alert (N=449)	p-value
Primary Outcome			

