- If children are involved, what is the investigator's assessment of the overall risk level for the children participating in this study? N/A
- Include an appropriate Data and Safety Monitoring Plan. Examples of DSMPs are available here <http://your.yale.edu/policies-procedures/forms/420-fr-01-data-and-safety-monitoring-plans-templates-for>
 - Minimal risk
 - Greater than minimal

Optimizing Electronic Alerts for Acute Kidney Injury
Data and Safety Monitoring Plan
420 FR.1
PI: F. [name] MSCE

The principal investigator is responsible for monitoring the data, assuring protocol compliance, and conducting the safety reviews biannually. During the review process the principal investigator will evaluate whether the study should continue unchanged, require modification/amendment, or close to enrollment. The principal investigator and the Institutional Review Board (IRB) have the authority to stop or suspend the study or require modifications.

Based on new information obtained from our recent general AKI alert study, we are taking necessary precautions to maximize patient safety in this trial. While we still feel that this is a minimal risk trial, we plan to have a Data Safety Monitoring Board review our results at an interim analysesat 50% enrollment across our four teaching hospitals. Any signal of harm will suspend the study to further enrollment.

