A group sequential design with Hwang-Shih-DeCanli spending functions with gamma = -4 for the efficacy boundary and gamma = -2 for the futility boundary with two interim analyses will be utilized and a two-sided Cochran-Mantel-Haenszel (CMH) method will be used for the sample size calculation to account for the four hospitals. Our preliminary data suggests that 18.2% of patients would experience the primary outcome of progression of AKI, dialysis, or mortality. We determined that a relative 20% reduction to 14.6% would be clinically significant. A total sample size of 4600 patients (i.e., 2301 per group) achieves at least 90% power to detect this degree of change. The alpha significance level of the test was set at 0.05. We will increase this

number by 10% to account for potential contamination of the effect across study arms, leading to a final sample size of 5060 individuals with a breakdown as follows based on relative numbers of beds in each hospital:

Yale New Haven Hospital: 2447

St. Raphael's Campus: 1214

Bridgeport Hospital: 910

Greenwich Hospital: 489

We will compare the rates of the primary outcomes between the intervention arm and the control arm using the chi-square test with Cochran-Mantel-Haenszel correction for the 4 study strata based on the hospital.. We will also perform exploratory analyses examining patients within the three medication categories to assess whether discontinuation rates differ by medication and, importantly, what clinical impact is apparent from alerting for those particular agents. Finally, should alerting show a clinical benefit, we will perform a mediation analysis to determine what fraction of that benefit (if any) can be attributed to medication cessation.

In addition, a retrospective examination will be performed to assess improvement in the control group before / after intervention as a measurement of contamination. We expect that providers who receive AKI alerts on some patients may be more likely to look for AKI in other patients, potentially diluting the effect of the intervention – this pre/post intervention analysis will help in assessing that level of contamination.

Because we are enrolling patients across four sites, we will do an exploratory analysis to determine the efficacy of alerts independently at each hospital.

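### The expected harms of stopping each drug class are left to DSMB monitoring and absent from the outcome list and final analysis, so a positive trial need not report them by arm on the full data

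*Combined protocol and SAP*

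**What the plan says.** Section 10 (Risks) acknowledges that the alert may cause useful drugs to be stopped. For each class it tabulates the risks and an "associated monitoring plan to ensure that differential discontinuation does not cause harm to patients". The risks include more opioid use and worse pain, hypertension, pulmonary edema and heart failure, and GI bleeding and severe anemia. The measures are opioid exposure per patient-day, naloxone or naltrexone, intubation, nursing-reported pain, blood pressure, chest X-ray, echocardiogram, transfusion and endoscopy.

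Section 11 (Minimizing Risks) repeats that "the internal DSMB has identified outcomes of interest for each of the medication classes" and lets the DSMB suspend an arm if it detects harm.

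Section 4 (Study Outcomes) sets a primary composite of AKI progression, dialysis or death within 14 days and a main secondary outcome of drug cessation. It then continues: "Other secondary study endpoints will look at a variety of patient outcomes as well as best practice metrics, including the following". That list covers mortality, dialysis, AKI stage and duration, readmission, cost and AKI care processes.

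Section 12 has the DSMB "review our results at an interim analysesat 50% enrollment across our four teaching hospitals", with any harm signal halting enrolment. Section 13 gives p-value limits for efficacy (.0042) and futility (.8952), and none for harm. It also plans exploratory analyses within the three drug classes and, if the alert shows benefit, a mediation analysis through drug cessation.

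**The concern.** The alert is meant to get drugs stopped, and the protocol itself says what stopping them may cost. Those costs are not outcomes. The primary composite counts kidney events and death, so the alert could lower it while raising opioid use, bleeding or heart failure, and the prespecified results would not have to show this.

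The plan is also lopsided: a benefit would be traced back to drug cessation by mediation analysis, but no listed analysis estimates what cessation cost. Section V expects positive results to lead to wider adoption. Section 3 reports signals of harm at two hospitals in the group's previous alert trial and argues that even apparently harmless alerts need rigorous evaluation.

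**Working it through.** **1. Where the section 10 measures appear**

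| Place | Are the measures named? |
|---|---|
| Section 10, risk table | Yes, for monitoring |
| Section 11 | Referred to as a group, for the DSMB |
| Section 4, outcomes | No |
| Section 12, monitoring plan | No |
| Section 13, analyses, subgroups, interim | No |

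Only one DSMB look is dated, at 50% enrolment. (Section 13 mentions two interim analyses in its design sentence but describes one.) Section 12 also has the principal investigator review safety twice a year. Section 4 keeps all investigators blinded until the trial ends, so if blinding holds, that review cannot compare arms.

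**2. The plan's own sample size**

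Inputs from section 13: "The alpha significance level of the test was set at 0.05"; a "two-sided Cochran-Mantel-Haenszel (CMH) method will be used for the sample size calculation"; "18.2% of patients would experience the primary outcome of progression of AKI, dialysis, or mortality"; a "relative 20% reduction to 14.6% would be clinically significant"; 90% power.

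n per arm = [1.960√(2p̄q̄) + 1.282√(p₁q₁ + p₂q₂)]² / (p₁ − p₂)²

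With p₁ = 0.182, p₂ = 0.146 and p̄ = 0.164, this gives 2222 per arm, 4444 in total. Continuity correction gives 2277 per arm, 4554 in total. A simulated group sequential factor of 1.0416 for one look at 50% gives 4444 × 1.0416 ≈ 4629. The stated 4600 is therefore reproduced, and 4600 × 1.10 = 5060. It is sized for the primary composite; no rate or margin is stated for any harm. I use 5060 throughout, although section III gives 4592.

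**3. What the second half of the data adds**

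The documents give no harm rates, so the control rates p₁ here are assumptions. With d = p₂ − p₁, power is Φ{[d − 1.960√(2p̄q̄/n)] / √[(p₁q₁ + p₂q₂)/n]}. Setting it to 0.80 gives the smallest detectable increase d, in percentage points:

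| Assumed control rate | 50% look, 1265 per arm | Full data, 2530 per arm |
|---|---|---|
| 2% | 1.9 | 1.3 |
| 5% | 2.7 | 1.9 |
| 10% | 3.6 | 2.5 |
| 20% | 4.6 | 3.2 |

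For 5% against 7%, power is 56% at the look and 85% on the full data.

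**4. Drug class and analysis population**

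Section 3 gives exposure at AKI onset in the preliminary cohort: NSAID 4.2%, RAAS 18%, PPI 39%. Eligibility requires at least one class, so each share is divided by the proportion exposed to any class. That proportion is 4.2 + 18 + 39 = 61.2% if classes never overlap, and 39% if every NSAID and RAAS user also takes a PPI. The overlap is not given, so these are the two extremes. If a measure were read only across whole arms, an effect confined to its class would shrink by one over the share.

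| Class | Share of enrolled | Dilution if read across whole arms |
|---|---|---|
| NSAID | 4.2/61.2 = 6.9% to 4.2/39 = 10.8% | 14.6- to 9.3-fold |
| RAAS | 18/61.2 = 29% to 18/39 = 46% | 3.4- to 2.2-fold |
| PPI | 39/61.2 = 64% to 39/39 = 100% | 1.6- to 1.0-fold |

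NSAID users would number 5060 × 4.2/61.2 = 347 to 5060 × 4.2/39 = 545, or about 174 to 272 per arm (87 to 136 at the 50% look). At an assumed 5% control rate, the detectable increase among them is 6.6 to 8.7 points on the full data and 10.2 to 13.6 points at the look.

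As an illustration, a 10-point rise among NSAID users would appear across whole arms as 10 × 0.069 = 0.7 to 10 × 0.108 = 1.1 points. That is below the 1.3 points detectable at the end even at a 2% control rate.

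**The case against.** A reader might infer that the named harms are never compared between arms. The documents do not support that. Monitoring for harm from differential discontinuation, with authority to suspend an arm, implies that the DSMB looks at the arms side by side. What is missing is the method, the population, the threshold and any commitment to report the result.

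A reader might also infer that the measures will be read across whole arms, so that class-specific effects are washed out. The plan does not say so. The section 10 table is organised by class, and section 13 plans by-class analyses of the clinical impact of alerting and lists exposure to each class as a subgroup. The dilution figures are therefore conditional. The large one applies to NSAIDs only; transfusion and endoscopy sit in the PPI row, where dilution is small. The by-class analyses are exploratory, however, and name none of the harms.

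Other protections exist. Adverse events go to the monitors within 5 days. Mortality, readmission and cost are listed endpoints that could catch some serious consequences. The wording that opens the secondary list does not strictly close it. Section V's remark on adoption describes potential benefit and is not a decision rule. All of this stands, but none of it commits the trial to a by-arm estimate of opioid exposure, transfusion or the other measures on the full data. A fuller DSMB charter may exist; these documents do not contain one.

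Finally, the full-data comparison would still miss a moderate harm in NSAID users. That is true, and it is a reason to report estimates with intervals rather than rely on tests.

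**Conclusion.** The concern holds as a gap in prespecification and reporting. The plan can be followed exactly and yield no full-data, by-arm estimate of the harms that it expects from its own intervention. It does not establish that arms go uncompared during the trial, or that class-specific effects will be diluted.

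If harm measures were compared at the 50% look alone, the detectable increase would be about 2.7 points rather than 1.9 at an assumed 5% control rate; comparing on the full data lowers it by roughly 30%. These figures rest on assumed harm rates and 1:1 allocation of 5060 patients. The by-class figures also assume that the section 3 exposure shares carry over to the trial. The primary analysis and its sample size are unaffected. The change should be made, because it is cheap and lets the trial weigh kidney benefit against the cost of stopping the drugs.

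**What to change.** Add the section 10 measures to section 4 as prespecified safety outcomes and to section 13 as a planned analysis. Compare alert with usual care on all enrolled patients, from randomisation to discharge or day 14, with the exact window stated. Do this overall and, for each measure, within patients exposed to the relevant class at randomisation. Exposure is fixed before allocation, so the within-class comparison remains a randomised one. Report risk differences for events and mean differences for continuous measures such as opioid exposure and pain score, with confidence intervals. Use the same by-class tables for the DSMB, and state there the comparison and population to be used.

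The cost is protocol wording and extra tables from measures already intended for DSMB monitoring. Alpha and the 5060 target stay as they are. The downside is imprecision for NSAIDs, with about 350 to 545 exposed patients over both arms, so an unremarkable NSAID result should not be read as showing that there is no harm.

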7. **Subject classification:** Check off all classifications of subjects that will be specifically recruited for enrollment in the research project. Will subjects who may require additional safeguards or other considerations be enrolled in the study? If so, identify the population of subjects requiring special safeguards and provide a justification for their involvement.

 Children	 Healthy	 Fetal material, placenta, or dead fetus
 Non-English Speaking	 Prisoners	 Economically disadvantaged persons
 Decisionally Impaired	 Employees	 Pregnant women and/or fetuses
 Yale Students	 Females of childbearing potential	

NOTE: Is this research proposal designed to enroll children who are wards of the state as potential subjects?

Yes No

8. **Inclusion/Exclusion Criteria:** What are the criteria used to determine subject inclusion or exclusion?

See above.

9. How will **eligibility** be determined, and by whom? Eligibility will be assessed electronically, without human intervention, within the Epic best practice alert framework as built by JDAT. Those that meet the inclusion criteria and who have no exclusion criteria will be automatically enrolled and randomized.

10. **Risks:** Describe the reasonably foreseeable risks, including risks to subject privacy, discomforts, or inconveniences associated with subjects participating in the research.

The risks to subjects in these trials is minimal, as the studies randomize them to usual care versus an alert that simply synthesizes data that is already present in the medical record. Potential risks include:

- Loss of confidentiality, as we will be collecting patient information and data.
- Overtreatment: If alerts affect physician behavior, then patients randomized to an alert arm may be more likely to undergo certain tests or interventions such as fluid boluses. These interventions fall within the standard-of-care and may benefit patients, but it is also possible that additional interventions may not benefit patients and could incur additional costs.

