- Where appropriate, how will pertinent information be returned to, or shared with subjects at a later date? The results of this study will not be pertinent to the subjects, as the effect of the alert is expected to be transient and should have no impact on their future quality of life beyond that measured by the outcome of the study itself. Moreover, post-hoc disclosure of the nature of the study to the subjects may generate undue stress and concern on the part of the subject as to the quality of their overall clinical care. As most patients are not familiar with AKI, informing them to the presence of the disease without offering a tangible benefit may further increase anxiety surrounding their overall health. We will update all clinicians of the results of this trial after trial completion. We are not collecting data that would tie a specific clinician to an outcome. For example, while we would inform clinicians that the alerts decreased the use of certain drugs, we will not be able to tell them what their specific rate of drug continuation or discontinuation would be.

SECTION IV: PROTECTION OF RESEARCH SUBJECTS

Confidentiality & Security of Data:

1. What protected health information (medical information along with the HIPAA identifiers) about subjects will be collected and used for the research? Patient Name, SSN, zip code, DOB, Admission/discharge dates, medical record number, laboratory values, provider notes, medical procedures, medical history, medication lists, imaging results.
2. How will the research data be collected, recorded and stored? All data, both patient and provider, will be collected electronically by an automated algorithm that interfaces with the EPIC user database system, developed by JDAT. Data will be skimmed from the EHR, processed electronically, encrypted, deidentified, and transferred to a secure server for storage and later analysis. As discussed above, the primary dataset will contain no PHI. We will maintain a separate “linking file” that contains all PHI and will be stored on a separate server to limit the risk of accidental disclosure. The linking file is being maintained for potential future linking to national databases of death and dialysis.

3. How will the digital data be stored? CD DVD Flash Drive Portable Hard Drive Secured Server Laptop Computer Desktop Computer Other

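### For pulmonary edema, heart failure, GI bleed and severe anemia, the safety table lists only tests, procedures or treatments, with no findings and no hemoglobin, so extra testing and harm may be hard to separate

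*Combined protocol and SAP*

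**What the plan says.** The under-treatment table in Section I, 10 (Risks) pairs the risks of stopping each drug class with a monitoring plan.

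- **NSAID.** Risks: "Increased use of opioid analgesics -Worse pain". Monitoring: "Morphine-equivalent opioid exposure per patient-day -Use of naloxone and/or naltrexone -Intubation -Nursing-reported pain score".
- **ACE/ARB/renin.** Risks: "Hypertension -Pulmonary Edema -Heart Failure". Monitoring: "Blood pressure -Intubation -Chest X-Rays".
- **PPI.** Risks: "GI Bleed -Pain -Severe anemia". Monitoring, as the text was extracted: "Echocardiogram -Blood Transfusion -Endoscopy Procedures -Nursing-reported pain score". The echocardiogram probably belongs to the ACE/ARB/renin row and was displaced at a page break. It is treated here as a heart-failure item, and its position is not counted as an error.

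The overtreatment bullet in the same section says that "patients randomized to an alert arm may be more likely to undergo certain tests or interventions such as fluid boluses".

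Section I, 11 (Minimizing Risks) says that the DSMB chose these outcomes class by class and may suspend an arm if it detects harm. Sections I, 11 and 12 add that any harm signal at the 50% interim analysis halts enrollment. The Interim Analysis text in Section I, 13 gives numerical limits for efficacy and futility but none for harm.

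Section IV (Confidentiality & Security of Data, item 1) lists among the data to be collected "laboratory values, provider notes, medical procedures, medical history, medication lists, imaging results".

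**The concern.** The intervention acts on clinicians. A safety measure that also depends on what clinicians choose to order can differ between arms for two reasons: patients were harmed, or they were watched more closely. The plan itself foresees the second.

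Pulmonary edema, heart failure, GI bleed and severe anemia are among the most serious harms named, and none of them has a measure based on a result. More chest X-rays in the alert arm could reflect diligence. Equal numbers of X-rays or endoscopies would not show that edema or bleeding was equally common. Intubation and transfusion lie closer to the harm, but they register mainly severe or treated cases and also follow from a clinical decision. Severe anemia is defined by a laboratory value, yet transfusion is the only item that bears on it.

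The board's ability to judge whether stopping these drugs hurts patients is at stake. Section I.10 uses stopping a PPI in a patient with a gastrointestinal bleed as its own example of possible danger, and that harm falls in the gap.

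**Working it through.** The plan states no figure on this point, so there is none to reproduce. The check is a classification of the table, then two calculations for scale.

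**1. Harms against measures** (the matching of items to harms is mine)

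| Class | Harm named | Items bearing on it | Direct measure? |
|---|---|---|---|
| NSAID | More opioid use | Opioid exposure; naloxone/naltrexone; intubation | Yes |
| NSAID | Worse pain | Pain score | Yes |
| ACE/ARB/renin | Hypertension | Blood pressure | Yes |
| ACE/ARB/renin | Pulmonary edema | Chest X-ray; intubation | No |
| ACE/ARB/renin | Heart failure | Echocardiogram; chest X-ray; intubation | No |
| PPI | GI bleed | Endoscopy; transfusion | No |
| PPI | Pain | Pain score | Yes |
| PPI | Severe anemia | Transfusion | No |

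Result: 4 of 8 harms have a direct measure and 4 do not.

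**2. Entries by type.** There are 4 + 3 + 4 = 11 entries. Four are direct measures (opioid exposure, blood pressure, pain score twice). Four are treatments or clinical events (naloxone/naltrexone, intubation twice, transfusion). Three are tests or procedures (chest X-ray, echocardiogram, endoscopy). For those three the table does not say whether use or finding counts.

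**3. Does other text fill the gap?** The Data and Safety Monitoring Plan in Section I.12 defines none of the items and gives no time window or denominator. Section I.13 says that guidelines on harm will go to the DSMB, but does not give them.

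**4. Illustration: could a rise in ordering alone look like a difference?** Final sample size is 5060 (Section I.13). At 50% enrollment this is 5060 / 2 / 2 = 1265 per arm. The ordering rates and the 5% two-sided criterion are assumptions; neither is in the documents. With no true harm, the chance of p < 0.05 is about

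Φ( |p1 − p0| / √{[p0(1 − p0) + p1(1 − p1)] / n} − 1.96 ).

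For p0 = 0.30 and p1 = 0.33, the standard error is √[(0.2100 + 0.2211) / 1265] = 0.0185. Then z = 0.03 / 0.0185 ≈ 1.63, and Φ(1.63 − 1.96) ≈ 0.37.

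| Assumed control rate | 10% relative rise | 20% relative rise |
|---|---|---|
| 10% | 0.13 | 0.36 |
| 30% | 0.37 | 0.90 |
| 50% | 0.71 | >0.99 |

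**5. Patients per class at the interim.** Section I.3 gives recent exposure at AKI onset as 4.2% NSAID, 18% RAAS and 39% PPI. The share of eligible patients lies between no overlap (divide by 4.2 + 18 + 39 = 61.2) and full overlap (divide by 39).

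- NSAID: 6.9% to 10.8%, or 87 to 136 per arm.
- RAAS: 29% to 46%, or 372 to 584 per arm.
- PPI: 64% to 100%, or about 806 to 1265 per arm.

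GI bleed and severe anemia therefore concern the largest class. NSAID users are too few for comparisons within that class to stand alone for rare events.

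**The case against.** Much of the table is sound. Eight of 11 entries are not tests or procedures, and the ACE/ARB/renin cell opens with blood pressure, a direct measure of hypertension. Intubation and transfusion are clinical consequences. The table does not say that imaging is merely counted, and imaging results are collected. The alert steers clinicians to medication review, not to imaging or endoscopy; the plan's only example of overtreatment is fluid boluses. The prior general alert changed no process measure (Section I.3), although it was a different alert.

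These points stand, and they rule out several stronger conclusions that a reader might infer:

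- **That the whole table counts orders instead of harms, or that the DSMB cannot detect harm at all.** The classification contradicts the first. Intubation and transfusion, whatever their limits, contradict the second.
- **That extra testing would suspend the trial with probability 0.37 or similar.** No passage sets p < 0.05, or any threshold, for these items. Suspension of an arm is left to the DSMB's judgement. In Section I.10 the prior trial's harm signal was a raised relative risk of the primary outcome. The probabilities above describe an assumed comparison, not a stopping rule.
- **That an NSAID effect would be diluted 9- to 15-fold** (1 / 0.108 to 1 / 0.069). This assumes that class-specific items are pooled across whole arms, which no passage says. The outcomes were chosen by class, and Section I.13 plans exploratory analyses within the medication categories, though it does not tie them to this table.

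None of this supplies a finding-based measure for the four harms, or a hemoglobin value.

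**Conclusion.** The point holds for four of the eight named harms. For pulmonary edema, heart failure, GI bleed and severe anemia, the plan lists only items that depend on clinician decisions, in a trial of an alert that may alter those decisions. For these four the DSMB may not be able to tell more testing from more harm. The defect is one of missing definitions and one missing laboratory measure; it does not show that monitoring as a whole fails.

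No effect on error rates or stopping can be derived from the documents. The illustration shows only that, at interim numbers, a modest rise in a common test could produce a nominal difference without harm. The conclusion assumes that no document outside this protocol, such as the guidelines promised to the DSMB, already defines these outcomes by findings.

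**What to change.** Amend the monitoring table in Section I.10, using the data listed in Section IV:

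1. **Severe anemia and GI bleed.** Beside transfusion and endoscopy, add post-randomization hemoglobin over a fixed window: the lowest value and the change from the last pre-randomization value. Report the number of measurements by arm, because more frequent draws tend to give lower minima. State how patients discharged before the window ends are handled.
2. **Pulmonary edema and heart failure.** Report imaging findings by arm next to the number of tests done, so that a rise in testing alone can be recognised. Apply the same rule for reading report text in both arms.
3. **Denominator and scale.** Show each class-specific item among patients on that class at randomization, in addition to the whole-arm comparison. Keep opioid exposure, blood pressure and pain score continuous.

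No new patients are needed. No new data collection is needed either, provided that hemoglobin and imaging report text are within the listed laboratory values and imaging results. The cost is extra programming and some misclassification from report text. Some dependence on testing frequency will remain, since edema is seen only when imaging is done; reporting test numbers alongside makes that visible but does not remove it.
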